- ii. If requesting a waiver of **signed** authorization, describe why it would be impracticable to obtain the subject's signed authorization for use/disclosure of this data: We are preparing for a trial that meets a framework for consent in cluster randomized trials that recommends a waiver of informed consent of patients if the following conditions are met: (1) the intervention is at the level of the hospital and informed consent of large numbers of individual patients in the hospital is not possible; (2) the study meets the Common Rule criteria for waiver of informed consent (see Section 5.ii above) and (3) participants are approached after randomization with information on the intervention. Also this study uses no investigational agents or devices, and simply attempts to implement giving a single dose of an evidence-based, FDA-approved medication in a hospital setting with referral to treatment to appropriate adult OUD subjects. During software development stage there is minimal risk to the clinician in giving input on the software's format and content.

The investigator assures that the protected health information for which a Waiver of Authorization has been requested will not be reused or disclosed to any person or entity other than those listed in this application, except as required by law, for authorized oversight of this research study, or as specifically approved for use in another study by an IRB.

Researchers are reminded that unauthorized disclosures of PHI to individuals outside of the Yale HIPAA-Covered entity must be accounted for in the "accounting for disclosures log", by subject name, purpose, date, recipients, and a description of information provided. Logs are to be forwarded to the Deputy HIPAA Privacy Officer.

6. **Process of Consent/Accent:** Describe the setting and conditions under which consent/assent will be obtained, including parental permission or surrogate permission and the steps taken to ensure subjects' independent decision-making.

We will be requesting a waiver of consent for all clinicians for the duration of this trial. Clinicians participating in both the control sites and the intervention sites will be given an information sheet prior to participation. All clinicians in the practice will be forwarded the information sheet. We will also utilize an e-mail notification system. OUD patients would not be considered human subjects in the case of this trial.

7. **Evaluation of Subject(s) Capacity to Provide Informed Consent/Accent:** Indicate how the personnel obtaining consent will assess the potential subject's ability and capacity to consent to the research being proposed.

As practicing clinicians, these subjects have capacity to make medical decisions as a part of their daily lives. Therefore, they also have capacity to consent.

8. **Non-English Speaking Subjects:** Explain provisions in place to ensure comprehension for research involving non-English speaking subjects. If enrollment of these subjects is anticipated, translated copies of all consent materials must be submitted for approval prior to use.

Research will only be conducted with English speaking subjects

As a limited alternative to the above requirement, will you use the short form* for consenting process if you unexpectedly encounter a non-English speaking individual interested in study participation and the translation of the long form is not possible prior to intended enrollment? YES NO Not Applicable

9. **Consent Waiver:** In certain circumstances, the HIC may grant a waiver of signed consent, or a full waiver of consent, depending on the study. If you will request either a waiver of consent, or a waiver of signed consent for this study, complete the appropriate section below.

Not Requesting any consent waivers

Requesting a waiver of signed consent:

Recruitment/Screening only (if for recruitment, the questions in the box below will apply to recruitment activities only)

Entire Study (Clinicians participating in the study will be given an information sheet in place of written consent)

For a waiver of signed consent, address the following:

- Would the signed consent form be the only record linking the subject and the research? YES NO
- Does a breach of confidentiality constitute the principal risk to subjects? YES NO
OR
- Does the research pose greater than minimal risk? YES NO
- Does the research include any activities that would require signed consent in a non-research context? YES NO

Requesting a waiver of consent:

Recruitment/Screening only (if for recruitment, the questions in the box below will apply to recruitment activities only)

Entire Study (Clinicians participating in the study will be given an information sheet in place of written consent)

For a full waiver of consent, please address all of the following:

- Does the research pose greater than minimal risk to subjects?

Yes *If you answered yes, stop. A waiver cannot be granted.*

No

- Will the waiver adversely affect subjects' rights and welfare? YES NO

- Why would the research be impracticable to conduct without the waiver? Yes

As this is a Pragmatic Trial focused on implementing this intervention in a way that is as close to routine care as possible, it would be impractical to request consent from each clinician. We will be applying for a waiver of consent for this population. It would be a deterrent for clinicians to participate in this intervention with the added complications of consent. Additionally, clinician stigma to treating individuals with OUD could bias the sample if clinicians that have a stronger stigma toward these patients can refuse to participate. For this reason and since clinician data will be de-identified and unavailable to the investigators, we propose a waiver of consent of the clinicians to ensure the scientific validity of the CDS intervention to overcome barriers to adoption of this practice. There is precedent for such a waiver in a similar situation, Suffoletto et al. The Effect of a Statewide Mandatory Prescription Drug Monitoring Program on Opioid Prescribing by Emergency Medicine Providers Across 15 Hospitals in a Single Health System. *J Pain.* 2018;19(4):430-8

- Where appropriate, how will pertinent information be returned to, or shared with subjects at a later date?

OUD patients: As OUD patient data will not be used, there will be no findings that would be reportable to this population. In an effort of good faith, we will incorporate a broadcast system in the ED with approved IRB text to be used locally at each site as they see fit (i.e., posters, screen savers, information sheets).

Clinicians: Clinicians will be made aware of study findings by use of a broadcast e-mail to all participating sites referencing the ClinicalTrials.gov record as well as notification of publications to open-access journals and articles attributable to the study, in which results of the study will be disseminated.

SECTION IV: PROTECTION OF RESEARCH SUBJECTS

Confidentiality & Security of Data:

1. What protected health information (medical information along with the HIPAA identifiers) about subjects will be collected and used for the research?

No patient private information will be collected.

2. How will the research data be collected, recorded and stored?

OUD patients: OUD private information will not be collected. Patients will instead be identified with a unique study identifier that The Honest Broker in each system could in theory, link to patient data. Identifiers may be system-dependent, but it will be mandatory that the identifier which is used is not an identifiable piece of protected health information (PHI) and that special administrative access is required to the local EHR to use this identifier to link back to patient data. Further, we will not be collecting or considering the actual date of OUD patient visit, but rather, we will collect the day on

which the OUD patient visited (i.e. Day 42 of the trial) without knowing the exact start date for each site. As such, we would not be able to link a visit day with a OUD patient.

Clinicians: We intend to integrate the use of an Honest Broker for each health system to de-identify the specific sites in which this trial is taking place and data is being collected. The Honest Broker for each external health system will remove all identifiers and be responsible for the key to the identifiers.

3. How will the digital data be stored? CD DVD Flash Drive Portable Hard Drive Secured Server Laptop Computer Desktop Computer Other
4. What methods and procedures will be used to safeguard the confidentiality and security of the identifiable study data and the storage media indicated above during and after the subject's participation in the study?

We will use study codes on data documents (e.g., completed questionnaire) instead of recording identifying information and keep a separate document that links the study code to subjects' identifying information locked in a separate location and restrict access to this document (e.g., only allowing primary investigators access). WE will encrypt identifiable data. Identifiable information will only be available to the PI and the Data Coordinating Center Co-I's. We will securely store data documents within locked locations and assign security codes to computerized records.

All portable devices must contain encryption software, per University Policy 5100. If there is a technical reason a device cannot be encrypted please submit an exception request to the Information Security, Policy and Compliance Office by clicking on url <http://its.yale.edu/egrc> or email [contact]

5. What will be done with the data when the research is completed? Are there plans to destroy the identifiable data? If yes, describe how, by whom and when identifiers will be destroyed. If no, describe how the data and/or identifiers will be secured.

Identifiable data will be destroyed within 6 months of study completion by the Principal Investigator.

6. If appropriate, has a Certificate of Confidentiality been obtained?

Yes, a COC will be provided as the study is funded by the NIH.

SECTION V: POTENTIAL BENEFITS

Potential Benefits: Identify any benefits that may be reasonably expected to result from the research, either to the subject(s) or to society at large. (Payment of subjects is not considered a benefit in this context of the risk benefit assessment.)

As there is minimal risk to the clinician subjects, the benefits substantially outweigh the risks. Potential benefits for the OUD patients are the possibility of initiating BUP for OUD as well as referral to ongoing medical treatment. This treatment has been shown to be effective for staying in treatment and decreasing mortality and efficacious to be initiated in the ED. Therefore, ED patients are likely to benefit greatly from treating their addiction and having the opportunity to rebuild their lives. Additionally, the CDS would benefit the emergency clinicians in terms of organization and identification of those within this subject population and streamlining initiation of treatment—which would otherwise likely be too medically and bureaucratically complex to be adopted into routine ED care. This system also provides

a mechanism to remove clinician stigma to the OUD population. This generalizable knowledge could be applied in healthcare system EDs nationally and internationally. Knowledge gained from this study will be invaluable towards better identifying and treating opioid use disorder and ED management of the population. Given the anticipated benefits to OUD patients and to society, the low risks are reasonable.

SECTION VI: RESEARCH ALTERNATIVES AND ECONOMIC CONSIDERATIONS

1. **Alternatives:** What other alternatives are available to the study subjects outside of the research?
OUD patients: consent will not be applicable for OUD patients as identifiers will not be collected. They will receive usual care.
Clinicians: Opt out and broadcast notification will be used. Clinicians will be informed of the research by broadcast. Posters targeting the clinicians with information about the study will be posted in all participating emergency departments. Additionally, the participating health systems will receive broadcast e-mails detailing the trial and the outcomes being studied as well as an explanation of the option and process to Opt out. That is, even though randomization is by site, clinicians at each site can opt out of using the intervention. Further, Clinical Champions identified at each site will discuss the intervention in the same way they would discuss any CDS being implemented in their EHR locally.
2. **Payments for Participation (Economic Considerations):** Describe any payments that will be made to subjects, the amount and schedule of payments, and the conditions for receiving this compensation.

There will be no payments for participation

3. **Costs for Participation (Economic Considerations):** Clearly describe the subject's costs associated with participation in the research, and the interventions or procedures of the study that will be provided at no cost to subjects.

Interventions will be provided at no cost. The only cost of participation is the time of the participant.

4. **In Case of Injury:** This section is required for any research involving more than minimal risk, and for minimal risk research that presents the potential for physical harm (e.g., research involving blood draws).
 - a. Will medical treatment be available if research-related injury occurs? **Not Applicable**
 - b. Where and from whom may treatment be obtained? **Not Applicable**
 - c. Are there any limits to the treatment being provided? **Not Applicable**
 - d. Who will pay for this treatment? **Not Applicable**
 - e. How will the medical treatment be accessed by subjects? **Not Applicable**

IMPORTANT REMINDERS

Will this study have a billable service? **Yes** **No**

A billable service is defined as any service rendered to a study subject that, if he/she was not on a study, would normally generate a bill from either Yale-New Haven Hospital or Yale Medical Group to the patient or the patient's insurer. The service may or may not be performed by the research staff on your study, but may be provided by professionals within either Yale-New Haven Hospital or Yale Medical Group (examples include x-rays, MRIs, CT scans, specimens sent to central labs, or specimens sent to pathology). Notes: 1. There is no distinction made

whether the service is paid for by the subject or their insurance (Standard of Care) or by the study's funding mechanism (Research Sponsored). 2. This generally includes new services or orders placed in EPIC for research subjects.

If answered, "yes", this study will need to be set up in OnCore, Yale's clinical research management system, for Epic to appropriately route research related charges. Please contact [contact]

Are there any procedures involved in this protocol that will be performed at YNHH or one of its affiliated entities?

Yes No

If Yes, please answer questions a through c and note instructions below. Not Applicable

IMPORTANT REMINDER ABOUT RESEARCH AT YNHH

Please note that if this protocol includes Yale-New Haven Hospital patients, including patients at the HRU, the Principal Investigator and any co-investigators who are physicians or mid-level practitioners (includes PAs, APRNs, psychologists and speech pathologists) who may have direct patient contact with patients on YNHH premises must have medical staff appointment and appropriate clinical privileges at YNHH. If you are uncertain whether the study personnel meet the criteria, please telephone the Physician Services Department at [contact]. **By submitting this protocol as a PI, you attest that you and any co-investigator who may have patient contact has a medical staff appointment and appropriate clinical privileges at YNHH.**

REFERENCES

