The need for flexibility in the graphical user interface of the intervention resulted in the decision to develop the CDS as a web application. This provides the ability to access the tool both embedded within the EHR or directly over the Internet. The web application was developed as a single-page application (SPA) based on React JavaScript library. The CDS is a user-initiated, SMART on FHIR (Substitutable Medical Applications and Reusable Technologies on Fast Health Interoperability Resources)[37] application that streamlines a flow diagram of our clinical protocol for ED-initiated BUP (Figure 2).

The intervention's graphical user interface (Figure 3) is an intuitive, simple layout presenting four care pathways in columns based on the patient's diagnosis of OUD, the severity of withdrawal, and readiness to start treatment. There is additional, optional decision support available for guidance to: 1) evaluate OUD severity based on DSM-5 criteria, 2) assess withdrawal severity using the clinical opiate withdrawal scale (COWS) score, and 3) motivate patient willingness and readiness to initiate MOUD treatment with a brief motivational interview.[38,39] These materials are also available to share with other members of the care team via a web address, text messaging, or QR code. The

interface also includes a toggle switch for the user based on whether or not they have a waiver to prescribe BUP. Non-waived clinicians cannot prescribe BUP but can administer a one-time dose of BUP in the ED for up to 72-hours.[\[40\]](#) When integrated into the local EHR system, launching a care pathway enables the user to: place orders, refer for ongoing MOUD treatment, and update clinical notes.

Buprenorphine (BUP) Initiation
Do you have a waiver to prescribe Buprenorphine?
No Yes

Buprenorphine Treatment Options

TEXT [contact]
WWW.WEBAADDRESSHERE.COM
QR CODE

Select from one of the four treatment options below

	Care Pathway #1	Care Pathway #2	Care Pathway #3	Care Pathway #4	Decision Support
Does the patient have Opioid Use Disorder?	Exit / No BUP No X (< 3 DSM Criteria)	Hold in ED Yes ✓ (>= 3 DSM Criteria)	Start 4 mg BUP (2x) Yes ✓ (>= 3 DSM Criteria)	Start 8 mg BUP Yes ✓ (>= 3 DSM Criteria)	Use these optional tools in any order to help you decide

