How severe is the patient's withdrawal?	None-to-Mild < 8 DO NOT give if intoxicated	None-to-Mild < 8 DO NOT give if intoxicated	Mild-to-Moderate 8 - 13	Moderate-to-Severe > 13	Diagnose OUD using DSM tool Assess withdrawal using COWS tool Motivate Readiness using interview tool
Is the patient ready to start treatment?	NO Select #1	YES Select #2	YES Select #3	YES Select #4	

The educational plan will be site-specific and tailored to the usual care at that institution. It will be administered within three months of the study start date. The details of the plan will be developed in partnership with local champions who self-identify an interest in helping to implement an ED-initiated BUP protocol at their site. Specifically, the education plan will be required to include:

1. A didactic on opioid use disorder, its diagnosis, assessment of withdrawal severity, and local resources for referral for ongoing MOUD treatment
2. Circulation and posting in each study site ED of the flow diagram of the study's clinical protocol for ED-initiated BUP (**Figure 2**). Since this protocol is considered best practice, clinicians at control sites will retain all control of their practice and be encouraged to follow this protocol even though the CDS will not be available to them.
3. Intervention sites will include strategies to increase use of the intervention by training clinicians on how to launch and use the CDS. Use of the intervention will be tracked with site-specific audit and feedback that is consistent with typical quality improvement initiatives at that site.

Given the ongoing and escalating opioid epidemic and wide scope of this trial, we anticipate that there may be concomitant interventions to stem OUD at study sites during the trial. We plan to permit these interventions as long as they are: (1) implemented before randomization so that they can be tracked and accounted for in the constrained randomization process, and (2) they are not a health IT intervention targeted at clinicians to initiate BUP in the ED.

Outcomes

The primary study hypothesis is that there will be higher rates of provision of ED-initiated BUP with referral for ongoing MOUD with user-centered CDS compared with usual care. Therefore, the primary outcome will be BUP initiation in the ED, defined as whether or not an eligible patient is administered

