BUP in the ED and/or prescribed BUP upon discharge from the ED. Although this is not a patient-centered outcome, it is a pragmatic and meaningful surrogate that will serve as a lead indicator of the CDS intervention's effect on engaging more OUD patients in treatment.

We will also evaluate the effect of user-centered CDS on the following secondary implementation outcomes as compared to usual care, including several following the RE-AIM framework:[\[41,42\]](#)

1. Referral to follow-up for ongoing MOUD treatment (patient-level; Y/N) treatment
2. Prescription for naloxone at ED discharge (patient-level; Y/N)
3. Receipt of discharge instructions on opioid use, overdose education, naloxone education, and buprenorphine education (patient-level; Y/N)
4. Clinician adoption rates (clinician level):
 - a. Provision of any ED-initiated BUP during the trial (Y/N)
 - b. Provision of any referral for ongoing MOUD treatment during the trial (Y/N)
5. Receipt of Drug Addiction Treatment Act of 2000 training during trial (clinician level; Y/N)

Additional secondary implementation outcomes to be obtained from the web application include: clinician fidelity with the intervention assessed via a critical action checklist[\[43\]](#) and error rate of the intervention (using surrogates based on tool usage, e.g., application launched but not used, launching a page in the web application and spending less than two seconds on that page). The intervention will continue to be made available for use after the trial concludes; three months after trial completion, medical record review of eligible patients will be conducted at a subset of intervention sites to determine the maintenance rate of the intervention.

Data Collection

Outcome data will be collected via SQL query of the local EHR at regular intervals from data routinely collected in each hospital's EHR. This will facilitate large-scale data collection that would not otherwise be practical in an explanatory trial.

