To enable consistent EHR data collection across sites, a master data dictionary of all data elements will be created. At each study site, the variables in the data dictionary will be validated against the institutional EHR to ensure that the variables are correctly mapped to the EHR field that corresponds to the clinical intent of the variable after accounting for documentation practices and workflow at each site.[\[47\]](#) In particular, the outcome variables of BUP initiated in the ED and referral made for ongoing MOUD treatment will be validated against the EHR to ensure accuracy. For data quality assurance, the mapped variables will be validated against the EHR to ensure that the data are clinically relevant to the goals of the project and correctly represents the clinical data that clinicians use to make decisions. Additionally, data to determine compliance, use, and fidelity with the CDS intervention that could not be reliably abstracted from the EHR (e.g., DSM-5 OUD score, COWS score) will be abstracted from the web application's use logs. Information on whether the patient attended the referred follow-up visit and whether the patient was prescribed BUP as an outpatient will be abstracted from the EHR if available (e.g., if the patient is seen for follow-up within the same system).

Data will be sent from study sites to the study DCC at predetermined, regular intervals. The DCC will conduct ongoing data monitoring activities on study data from all participating sites to ensure data received is what it is intended to be. Baseline data for the study participants will include demographic and clinical data such as age, gender, race, ethnicity, insurance status, past medical and psychiatric history, recent medical or psychiatric hospital admissions, recent enrollment in formal addiction treatment, active prescriptions for other opioids, and urine drug screen results as ascertained by regularly collected data in the EHR.

5. Genetic Testing N/A

6. **Subject Population:** Provide a detailed description of the types of human subjects who will be recruited into this study.

Subjects for this trial will be the clinicians in both the control sites and those sites implementing the user-centered CDS. A waiver of informed consent will be obtained for data collection of clinicians.

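### Referral is read from the EHR, and the CDS gives one arm an extra way to record it there, so part of a referral benefit could be better recording

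*Combined protocol and SAP*

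**What the plan says.** Source of outcomes (Section I, item 4, Data Collection): "Outcome data will be collected via SQL query of the local EHR at regular intervals from data routinely collected in each hospital's EHR". Among the secondary outcomes listed under Outcomes, the first is "Referral to follow-up for ongoing MOUD treatment (patient-level; Y/N"). Outcome 4b asks, for each clinician, whether any such referral was made during the trial. Referral also appears next to BUP initiation in the trial hypothesis (item 1, Statement of Purpose).

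What the CDS does (item 4, Intervention): once it is integrated in the local EHR, "launching a care pathway enables the user to: place orders, refer for ongoing MOUD treatment, and update clinical notes". Intervention sites also train clinicians to launch it, and "Use of the intervention will be tracked with site-specific audit and feedback".

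What control sites have: clinicians there receive the education and the flow diagram and are to "be encouraged to follow this protocol even though the CDS will not be available to them". Concomitant OUD interventions are allowed only if, among other conditions, "they are not a health IT intervention targeted at clinicians to initiate BUP in the ED".

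Safeguard (Data Collection): all data-dictionary variables are to be validated against each site's EHR, allowing for local documentation and workflow. BUP initiation and referral are singled out; the text ends "referral made for ongoing MOUD treatment will be validated against the EHR to ensure accuracy".

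**The concern.** The randomised intervention includes a tool that can produce the kind of record from which the outcome is read. Suppose clinicians in both arms refer equally often, but referrals made through the CDS reach a queryable field more reliably than those made by telephone, handout or free text. The query would then show a benefit where care did not differ.

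The other safeguards do not reach this problem:

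- The missing-data plan (item 13) deals with missing values. A referral made but not found would presumably be read as a No, although the coding rule is not stated.
- Constrained randomisation balances site factors before the intervention starts. It cannot balance a recording difference that the intervention creates afterwards.
- The GEE sensitivity analysis uses the same outcome data.
- Attendance at follow-up, a possible outside check, is taken from the EHR only where available.
- The chart review planned three months after the trial covers a subset of intervention sites only.

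At stake is the reading of a result that belongs to the stated hypothesis, although it is a secondary outcome.

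**Working it through.** The documents give no referral rate, capture rate, CDS uptake, intracluster correlation (ICC) or power figure for this outcome, so there is no stated figure to reproduce. What follows is an illustration with no true effect.

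**Inputs from the documents:** 20 EDs (item 8) allocated 1:1 (item 4, Design), so 10 per arm; two-sided alpha 0.05 (item 13).

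**Assumed inputs:** true referral rate p = 0.40 in both arms; query capture s0 = 0.60 without the CDS and s1 = 0.95 with it; uptake u, taken here as the share of intervention-arm referrals made through the integrated CDS; no false-positive referrals.

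**Formulas:**
- Observed control rate = p × s0 = 0.40 × 0.60 = 24.0%
- Capture in the CDS arm = s0 + u × (s1 − s0)
- Spurious difference = p × u × (s1 − s0)

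| Uptake u | CDS-arm capture | Observed CDS vs control | Spurious difference | Chance of p < 0.05 |
|---|---|---|---|---|
| 20% | 0.60 + 0.2 × 0.35 = 0.670 | 26.8% vs 24.0% | 2.8 points | 9% |
| 50% | 0.60 + 0.5 × 0.35 = 0.775 | 31.0% vs 24.0% | 7.0 points | 28% |
| 100% | 0.950 | 38.0% vs 24.0% | 14.0 points | 76% |

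The last column further assumes m = 100 patients per ED and an ICC of 0.05. The effective n per arm is 10 × 100 / (1 + 99 × 0.05) = 1000 / 5.95 = 168. At full uptake the standard error is √[(0.24 × 0.76 + 0.38 × 0.62) / 168] = 0.050, so the ratio is 0.14 / 0.050 = 2.8. A noncentral t with 18 degrees of freedom then gives 76%. This approximates, and is not, the planned GLMM.

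**Range over the true rate.** By the same formula, p = 0.20 gives 0.20 × 0.2 × 0.35 = 1.4 points at 20% uptake and 0.20 × 0.35 = 7.0 at full uptake. With p = 0.60 the figures are 4.2 and 21.0 points.

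**Range over the capture gap, p = 0.40.** Arm-average capture of 80% vs 80% gives no difference and 5% rejection. Capture of 80% vs 90% gives 32% vs 36%, a spurious 4 points; rejection is 8% to 21% for m from 40 to 200 and ICC from 0.02 to 0.10. Capture of 60% vs 90% gives 24% vs 36%, 12 points, and rejection of 36% to 94%.

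**Outcome 4b.** One captured referral is enough for a Yes. For a clinician with a single referral, capture of 60% vs 95% is a 35-point gap. With three referrals, assumed independent, it is 1 − 0.40³ = 93.6% vs 1 − 0.05³ = 99.99%, about 6 points.

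**The case against.** The best case against the point has four parts.

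- **The tool is optional and not exclusive.** It is user-initiated, can be opened over the Internet outside the EHR, acts in the EHR only when integrated, and clinicians may opt out. Control clinicians keep their usual functions, and education at every site covers local referral resources. This stands. A reader might infer that only the CDS creates these entries, or that using it always leaves one; the documents say neither. The bias needs only a difference in capture, and low uptake shrinks it.
- **Validation is already planned and allows for local documentation.** This stands in part. The general validation covers every dictionary variable, discharge instructions included. But the reference is the EHR itself, no comparison by arm is described, and its timing relative to go-live is not stated.
- **Easier referral is part of the intervention, so extra recorded referrals may be real.** This also stands. The difficulty is that the plan, as written, cannot separate extra referral from extra recording.
- **Chart review cannot find a referral that was never entered.** This is correct, and it limits what any fix can claim.

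**Conclusion.** The point holds for referral and, to a lesser degree, for outcome 4b. Part of a positive referral result could reflect recording. The size is unknown: the 2.8 to 14 points come from assumed rates, and equal capture would give none.

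Two stronger readings are not supported. A reader might extend the point to discharge instructions (secondary outcome 3), but the Intervention text does not list them among the CDS functions. The link could only be inferred from orders and notes, and the flow diagram is not shown in the text available. A reader might also doubt the primary outcome. BUP administered or prescribed should be less affected, because giving or prescribing a drug normally leaves a medication record in either arm; that is a judgement, not something the documents state. The point calls for a change to a secondary outcome and its validation, not to the trial's main comparison.

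**What to change.** 1. **Same sources in both arms.** Define referral from one set of EHR sources, namely orders, discharge paperwork and note text, and not only from a field that the CDS populates.
2. **Validate after go-live, by arm.** Carry out the planned referral validation at EDs of both arms once the CDS is live, on a random sample of eligible patients that includes query-negative ones. Report query sensitivity by arm and add a misclassification sensitivity analysis. With no false positives, the corrected rate is the observed rate divided by sensitivity: in the 20% uptake example, 0.268 / 0.670 and 0.240 / 0.600 both return 40%, provided every referral is somewhere in the chart. Include discharge instructions if the CDS turns out to affect them.
3. **Limit the wording.** Because referrals never entered cannot be recovered, state the conclusion as a difference in EHR-documented referral.

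The cost is protocol wording, a broader query and modest chart-review time. The review would have to be done locally, since the protocol commits to collecting no identifiable patient information. The reported referral effect may be smaller.
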